7.5. Statistical analysis

7.5.1. General considerations

Statistical analyses will be performed using SAS® v9.4 or higher (SAS Institute, Cary NC, USA).

Baseline demographic and other baseline characteristics, together with safety analyses will be performed on all participants who underwent the treatment phase. Baseline values are defined as the last valid value prior to treatment.

Where confidence limits are appropriate, a two-sided 95% confidence interval will be constructed.

7.5.2. Demographic and other baseline variables

Demographic and baseline condition related characteristics will be tabulated. Continuous variables will be summarized by a mean, standard deviation, minimum, median and maximum, and categorical variables by a count and percentage.

7.5.3. Safety analysis

Safety and tolerability will be assessed by review of all safety parameters, including adverse events. Serious adverse events, device-related SAEs, adverse events (by type and overall), device-related AE, adverse device reactions and device malfunction rates will be documented. Treatment tolerability, the number and percent of subjects who fail to complete the study and the number and percent of subjects who fail to complete the study because of adverse events will be presented. Time to withdrawal will also be assessed and presented by Kaplan-Meier curves.

7.5.4. Efficacy analysis

The efficacy endpoints will be assessed on evaluable treatments of qualifying attacks. The first use of the device is considered a training treatment and will not be included in the efficacy analyses. The first treatment of a qualifying attack after the training treatment is considered a test treatment and will be used for all efficacy assessments. If this treatment is not evaluable (i.e., no pain data at 2 hours post-treatment), a subsequent treatment of a qualifying attack with evaluable data will be considered the test treatment.

Use of rescue medication before the 2-hours assessment will be considered a treatment failure for the 2-hours endpoints, and before the 24 hours assessment for the sustained

Nerivio TCH-004 Clinical Study Protocol (NCT04089761)

Doc ID: TEC0105

Revision #: 1.0

Page: 37 of 49

24-hours endpoints. The percentage of participants achieving each of the efficacy outcomes will be presented in a tabular form along with two-sided 95% exact confidence intervals.

For the associated symptoms outcomes, the observed response proportions and corresponding 95% exact confidence intervals for each associated symptom will be provided. All patients with baseline and 2 hours values will be included in the analyses. A response in each associated symptom (nausea, vomiting, photophobia, phonophobia) is defined as change from presence of a specific associated symptom at baseline to absence of the same associated symptom at 2 hours post-treatment.

In addition, logistic regression models will be used to assess the efficacy. Baseline value and site will serve as covariates.

The first secondary endpoint (pain relief at 2 hours) may also be evaluated in attacks with aura and attacks without aura separately.

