	treatment will be considered a "training" treatment, aimed to verify the			
	participants use the device properly, and will only be included in the safety			
	analysis. The first treatment of a qualifying attack after the training treatment is considered a test treatment and will be used for all efficacy analyses. The			
	is considered a test treatment and will be used for all efficacy analyses. The			
	efficacy endpoints will be assessed on evaluable treatments of qualifying			
	attacks.			
	Phase III (optional) - Free-use: Participants who complete the treatment phase will be offered the opportunity			
	to participate in an 8-week free-use phase in which they will be able to			
	incorporate the Nerivio device into their usual care.			
Qualifying migraine	A qualifying migraine attack is defined as a migraine attack that:			
attack	was not preceded by another migraine attack or other headache			
attack	within the preceding 24 hours			
	was not preceded by the use of specific or non-specific acute			
	migraine medications within the previous 24 hours			
	3. occurred in a setting in which the patient could properly administer			
	the treatment (that is, it is possible to initiate a complete treatment			
	within 60 minutes of onset and the participant will be able to			
	complete the migraine diary at 2 hours after treatment)			
Primary endpoints	1. The safety of Nerivio			
i innary enuponits	The incidence of adverse events in general and by seriousness, severity			
	and association to the device.			
	2. Treatment tolerability			
	The percent of subjects who fail to complete the study because of adverse			
	events			
Secondary endpoint	Pain relief at 2 hours post-treatment:			
Occomulary emuporing	The proportion of participants achieving pain relief at 2 hours post-			
	treatment in the test treatment, with no use of rescue medication			
	2. Pain-free at 2 hours post-treatment:			
	2. I dill 1100 dt 2 110d13 post-trodutiont.			

Nerivio TCH-004 Clinical Study Protocol (NCT04089761)

Doc ID: TEC0105

Revision #: 1.0 Page: 10 of 49

	The proportion of participants achieving pain freedom at 2 hours post-			
	treatment in the test treatment, with no use of rescue medication			
	3. Disappearance of associated symptoms at 2 hours post-treatment			
	Disappearance of nausea in the test treatment at 2 hours post-treatment			
	II. Disappearance of phonophobia in the test treatment at 2 hours post-treatment			

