Caucasian, % (n/N)	86.5% (109/126)	88.9% (112/126)	
Triptan users, % (n/N)	51.6% (65/126)	44.4 (56/126)	
Migraine with aura, % (n/N)	, ,	, ,	
Often	30.2% (38/126)	26.2% (33/126)	
Rarely	20.6% (26/126)	23.8% (30/126)	
None	49.2% (62/126)	50.0% (63/126)	
MBS % (n/N)*	, ,	, ,	
None	3.2% (4/126)	0.8% (1/126)	
Nausea	29.4% (37/126)	24.6% (31/126)	
Photophobia	43.7% (55/126)	57.1% (72/126)	
Phonophobia	20.6% (26/126)	17.5% (22/126)	
Preventive medication use, % (n/N)	28.6% (36/126)	37.3% (47/126)	
Migraine attacks in the "roll-in" phase, n	440	437	
Treated migraine attacks in the "double-blind			
treatment" phase, n**	385	388	
Characteristics of the test treatment (mITT)			P value
Presence of aura in the "test treatment", % (n/N)†	19.2% (19/99)	19.4% (20/103)	0.96
Baseline pain severity in the "test treatment", %			
(n/N)†			0.11
Mild	35.4% (35/99)	41.7% (43/103)	0.11
Moderate	57.6% (57/99)	44.7% (46/103)	
Severe	7.1% (7/99)	13.6% (14/103)	
Presence of baseline associated symptoms in	7.176 (1766)	10.0% (1 11 100)	
the "test treatment", % (n/N)†			
Nausea	25.3% (25/99)	24.3% (25/103)	0.87
Photophobia	63.6% (63/99)	75.7% (78/103)	0.06
Phonophobia	55.6% (55/99)	56.3% (58/103)	0.91

^{*} Four participants in the active group reported allodynia as MBS (data not shown) **Participants were asked to treat up to four episodes †modifed intent-to-treat population

Nerivio TCH-004 Clinical Study Protocol (NCT04089761)

Doc ID: TEC0105

Revision #: 1.0

Page: 22 of 49

In the active group, 66.7% participants (66/99; $Cl_{95\%}$ 56.48-75.82) achieved pain relief for the test treatment, compared to 38.8% (40/103; $Cl_{95\%}$, 29.39-48.94) in the sham group, a therapeutic gain of 27.9% (p<0.001; Figure 4A). Similar results were found when missing data was imputed using a worst-case scenario (66/103=64.1% for active versus 41/104=39.4% for sham, p<0.001). Furthermore, more participants in the active group were pain-free at 2 hours post-treatment (37.4% [37/99; $Cl_{95\%}$ 27.85-47.67]) compared with the sham group (18.4% [19/103; $Cl_{95\%}$ 11.49-27.30]; a therapeutic gain of 19.0%; P=0.003, adjusted; Figure 4A). Rescue medication within 2 hours post-treatment was used by 1% of the participants in the active group and 3.8% in the sham group (p=0.19).

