6.4.2. Secondary endpoints

1. Pain relief at 2 hours post-treatment:

The proportion of participants achieving pain relief, defined as improvement from severe or moderate pain to mild or none, or improvement from mild pain to none, at 2 hours post-treatment in the test treatment, with no use of rescue medication

- 2. Pain-free at 2 hours post-treatment:
 - The proportion of participants achieving pain freedom, defined as improvement from mild, moderate, or severe pain to none, at 2 hours post-treatment in the test treatment, with no use of rescue medication
- 3. Disappearance of associated symptoms at 2 hours post-treatment
 - a. The proportion of participants reporting nausea at baseline and achieving absence of nausea at 2 hours post-treatment in the test treatment
 - b. The proportion of participants reporting phonophobia at baseline and achieving absence of phonophobia at 2 hours post-treatment in the test treatment
 - c. The proportion of participants reporting photophobia at baseline and achieving absence of photophobia at 2 hours post-treatment in the test treatment

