7.2.2. Secondary endpoints

Secondary efficacy endpoints include:

- Proportion of subjects reporting, for the test treatment, pain relief at 2 hours post treatment without use of rescue medication. Pain relief is defined as an improvement from severe or moderate pain to mild or no pain, or from mild pain to no pain.
- Proportion of subjects reporting, for the test treatment, pain-free at 2 hours post treatment without use of rescue medication. Pain free is defined as an improvement from mild, moderate or severe pain to no pain.
- Proportion of subjects reporting, for the test treatment, nausea at baseline and achieving absence of nausea at 2 hours post treatment without use of rescue medication.
- Proportion of subjects reporting, for the test treatment, phonophobia at baseline and achieving absence of phonophobia at 2 hours post treatment without use of rescue medication.
- Proportion of subjects reporting, for the test treatment, photophobia at baseline and achieving absence of photophobia at 2 hours post treatment without use of rescue medication.

Nerivio TCH-004 Clinical Study Protocol (NCT04089761)

Doc ID: TEC0105

Revision #: 1.0 Page: 35 of 49

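### As written, Section 7.5.4 keeps participants who did not have the symptom at baseline in the denominator of each associated-symptom disappearance rate, in conflict with a natural reading of 6.4.2 and 7.2.2

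*Combined protocol and SAP*

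**What the plan says.** Section 7.5.4 sets who enters the associated-symptom analyses: "All patients with baseline and 2 hours values will be included in the analyses". The next sentence defines success: "A response in each associated symptom (nausea, vomiting, photophobia, phonophobia) is defined as change from presence of a specific associated symptom", that is, present at baseline and absent 2 hours after treatment. Baseline presence therefore enters the definition of a response but not the definition of who is analysed. Each rate is reported with an exact 95% confidence interval.

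The endpoint definitions are worded differently. The synopsis says only "Disappearance of nausea in the test treatment at 2 hours post-treatment". Section 6.4.2 has "The proportion of participants reporting nausea at baseline and achieving absence of nausea at 2 hours post-treatment in the test treatment", and Section 7.2.2 has "nausea at baseline and achieving absence of nausea at 2 hours post treatment without use of rescue medication", with parallel wording for phonophobia and photophobia. None of these names a denominator separately.

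The mITT definition in Section 7.4 removes participants from an analysis when they have no valid assessment after baseline. It does not remove those who lacked the symptom. On rescue medication, 7.5.4 is general: "Use of rescue medication before the 2-hours assessment will be considered a treatment failure for the 2-hours endpoints".

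**The concern.** A participant who has no nausea at the start of the test attack, and who answers the nausea question at both times, meets the 7.5.4 inclusion sentence. That participant cannot move from present to absent and so is a fixed non-response. With such participants in the denominator, the reported figure is the share of the whole group who both had the symptom and lost it. It cannot exceed baseline prevalence, and it does not measure disappearance.

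This matters because the study has a single arm. There is no comparator with the same dilution, so the percentage and its interval are the whole result. Prevalence differs between symptoms, so equal resolution would look unequal, and nausea, the least common of the three in the adult study, would look worst. Two programmers, one following 7.5.4 and the other following 6.4.2, could both claim to follow the plan and report very different rates.

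**Working it through.** The plan states no expected rate or precision for these endpoints, so there is no figure of its own to reproduce. The calculation below only shows how far apart the two readings lie.

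**Inputs**
- N = 110, the size in Section 7.3, taken as participants with both values.
- Baseline prevalence p at the test treatment, from the adult pivotal study's active group (Section 4.2.2, Table 4): nausea 25/99 = 25.3%, phonophobia 55/99 = 55.6%, photophobia 63/99 = 63.6%. The documents give no adolescent figure, so using these is an assumption.
- Resolution r among those with the symptom: not given in the documents. Assumed 50%, with a range of 30% to 70%.

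**Formulas**
- Participants with the symptom: m = N × p, rounded.
- Responders: x = m × r, rounded.
- Rate as 7.5.4 is written: x/N. Restricted rate: x/m.
- Hence x/N = (x/m) × (m/N), which is resolution times prevalence.
- Intervals: exact (Clopper-Pearson) 95%.

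**Numbers put in**
- Nausea: m = 110 × 25/99 = 27.8, so 28; x = 14.
- Phonophobia: m = 110 × 55/99 = 61.1, so 61; x = 30.5, taken as 30.
- Photophobia: m = 110 × 63/99 = 70; x = 35.

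| Symptom | As 7.5.4 is written | Restricted to symptom at baseline | Ceiling as written (m/N) |
|---|---|---|---|
| Nausea | 14/110 = 12.7% (7.1 to 20.4) | 14/28 = 50.0% (30.6 to 69.4) | 25.5% |
| Phonophobia | 30/110 = 27.3% (19.2 to 36.6) | 30/61 = 49.2% (36.1 to 62.3) | 55.5% |
| Photophobia | 35/110 = 31.8% (23.3 to 41.4) | 35/70 = 50.0% (37.8 to 62.2) | 63.6% |

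Resolution is the same, apart from rounding, in all three rows. Yet as written the photophobia rate is 31.8/12.7 = 2.5 times the nausea rate.

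**Sensitivity to assumed resolution, 30% to 70%**
- Nausea: 7.3% to 18.2% as written, 28.6% to 71.4% restricted.
- Phonophobia: 16.4% to 39.1%, against 29.5% to 70.5%.
- Photophobia: 19.1% to 44.5%, against 30.0% to 70.0%.

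**Sensitivity to assumed nausea prevalence, at 50% resolution**
- At 15%, 40% and 60% prevalence the rate as written is 8/110 = 7.3%, 22/110 = 20.0% and 33/110 = 30.0%.
- The restricted rate is 50.0% each time (8/16, 22/44, 33/66).

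The direction does not depend on these choices: for any prevalence below 100%, and any resolution above zero, the rate as written is lower than the restricted one.

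**The case against.** The strongest reply is that the plan already implies the restricted denominator. Sections 6.4.2 and 7.2.2 speak of participants reporting the symptom at baseline, which a natural reading takes as the base population. The 7.5.4 sentence may be meant only as an observed-case rule, matching the mITT rule in 7.4. In the adult study (Section 4.2.2), freedom from the most bothersome symptom was reported over 81 and 88 participants, while relief of that symptom was reported over 95 and 99. The documents do not explain the smaller numbers, but they fit a rate not taken over everyone. Section 9.1 also mentions a separately kept statistical analysis plan, where the denominator may be named.

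Much of this stands. The restricted denominator is probably what is intended, and it would be wrong to infer that nothing in the protocol points to it. But the endpoint wording can equally be parsed as one joint condition, and the section that governs the analysis says otherwise. That is a conflict to correct.

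A reader might also draw stronger conclusions that the documents do not support:
- *Rescue users could count as responders, because 6.4.2 omits the rescue condition that 7.2.2 contains.* The failure rule in 7.5.4 covers the 2-hour endpoints without exception, so this is ruled out. The difference in wording is editorial.
- *Rescue users with no 2-hour symptom entry drop out and distort the rate.* In the adult study, "Rescue medication within 2 hours post-treatment was used by 1% of the participants in the active group and 3.8% in the sham group". Even if every rescue user lacked an entry, that is 28 × 1% = 0.3 to 28 × 3.8% = 1.1 of 28 participants with nausea. Losing one non-responder gives 14/27 = 51.9% instead of 50.0%.
- *The logistic models must fail.* The plan says "Baseline value and site will serve as covariates" but does not say that the baseline value is symptom presence, or that the models cover the symptom endpoints.
- *Vomiting is an unmeasured endpoint.* It appears only in the 7.5.4 list. It is neither among the per-attack symptoms in 6.3 nor an endpoint in 6.4.2 or 7.2.2, so it is a stray word.

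**Conclusion.** The point holds as a conflict between sections, with 7.5.4 the sentence at fault. Applied as written, it turns each disappearance rate into prevalence times resolution. Under the stated assumptions, that cuts a 50% nausea rate to about 13% and makes similar resolution look 2.5-fold different between nausea and photophobia. The sizes rest on adult active-arm prevalence carried over to adolescents, on an assumed resolution rate and on 110 participants with both values. The existence of the conflict rests on the text alone.

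A reader might infer that the study's conclusions are at risk. They are not: these are descriptive secondary endpoints with no success threshold, and the primary endpoints are safety and tolerability. What is at stake is a percentage that readers would misread and could not compare across symptoms.

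**What to change.** Replace the inclusion sentence in 7.5.4 with a rule to this effect: for each symptom, the denominator is mITT participants who had that symptom at baseline of the test treatment and have a 2-hour value, with rescue medication before 2 hours counted as failure, as 7.5.4 already provides. Report n/N for each symptom, so that the denominator and baseline prevalence are visible. As editorial tidying, carry the rescue condition of 7.2.2 into 6.4.2 and remove vomiting from the 7.5.4 list.

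No new data are needed: Section 6.3 already has participants record symptoms at both times and any medication taken. The denominator rule and the n/N display can be fixed before database lock in the statistical analysis plan, which Section 9.1 lists among documents that can change without a protocol amendment. Changing the endpoint wording in 6.4.2 is different, because 9.1 limits the notification-only route to changes unrelated to objectives or endpoints.

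The statistical cost is precision. At the adult rate about 28 of 110 participants would contribute to nausea. The interval for 14/28 is 38.7 points wide (30.65 to 69.35), against 13.3 points (7.14 to 20.43) for 14/110. The wider interval is the accurate one for disappearance, since only participants with the symptom carry information about it.

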7.5.5. Treatment by sites interaction

Poolability across centers may be assessed using logistic regression. Centers with less than 10 subjects will be grouped together by geographical area. If the center term is found significant (p<0.1), the reason for this interaction will be further explored. This evaluation may include demographic features, symptoms at presentation, clinical and treatment history, and site comparability in the features found to be associated with the primary endpoint variables. Adjustment for other covariates such as demographics or other baseline subject characteristics may be performed by adding these variables into a logistic regression model.

The analysis may be repeated for US sites vs. out of US (OUS) sites.

7.5.6. Handling of missing data

Sensitivity analyses of the efficacy endpoints may be performed to assess the impact of missing data of pain severity at 2 hours post-treatment on the efficacy outcomes. This will be performed using several possible imputation methods including, but not limited to:

- Observed data: use only treatments with non-missing pain data who did not withdraw early from study.
- Dropout/AE Imputation: a subject with no post baseline measurement of pain or a subject withdrawn due to an adverse event or treatment intolerability should be considered as a non-responder for this analysis.

Nerivio TCH-004 Clinical Study Protocol (NCT04089761)

Doc ID: TEC0105

Revision #: 1.0

Page: 38 of 49

 Worst Case Scenario: assumes that all subjects with missing pain data are failures.

 Best Case Scenario: assumes that all subjects with missing pain data are successes.

8. Data management

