The primary efficacy endpoint was the proportion of participants who achieved pain relief at 2 hours post-treatment in the "test treatment", defined as improvement from severe or moderate pain to mild or none, or, improvement from mild pain to none. The secondary efficacy endpoints pain-free (improvement from mild, moderate, or severe pain to none), MBS relief, pain relief & MBS relief, and MBS freedom at 2 hours post-treatment. Exploratory endpoints included 48-hour sustained pain-free and pain relief responses. An additional exploratory endpoint was within-subject consistency, defined as the proportion of participants achieving pain relief at 2 hours post-treatment in at least 50% of their treated attacks. Pain relief at 2 hours post-treatment as function of baseline pain level was also explored.

Results

296 participants were enrolled; 252 were randomized after the "run-in" phase, 126 were assigned to the active group and 126 to the sham group. Of the 44 who were not randomized, 33 failed to meet the "roll-in" criteria, 9 withdrew from the study and 2 were

Nerivio TCH-004 Clinical Study Protocol (NCT04089761)

Doc ID: TEC0105

Revision #: 1.0

Page: 21 of 49

withdrawn by the investigator due to migraine misdiagnosis. Among the 252 randomized participants (intent-to-treat population), 7 withdrew from the study, 3 (1 sham, 2 active) due to intolerance to the stimulation and 4 (2 sham, 2 active) were lost to follow up. 237 participants completed at least one treatment (the "run-in" treatment) and 203 participants completed the "test treatment". 202 participants (99 in the active group and 103 in the sham group) started the "test treatment" within one hour from symptom onset and reported pain level at 2 hours, forming the mITT population with evaluable data. 37 participants who did not complete the "test treatment", due to insufficient migraine attacks (n=18), participant's decision not to use the device (n=4), other (n=6) or unknown (n=9), were excluded from the efficacy analyses.

The demographic and clinical characteristics were similar between treatment groups (Table 4). The characteristics of treated migraine headaches were comparable to those reported in previous migraine studies [23–25].

Table 4: Demographic and clinical characteristics (intent-to-treat population)

Characteristic	Active group (n=126)	Sham group (n=126)	
Age, y (SD)	43.8 (12.25)	41.6 (11.81)	
Female, % (n/N)	80.9% (102/126)	80.9% (102/126)	

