7.3. Sample size

A sample size was calculated on the efficacy endpoint of pain relief at 2 hours post-treatment. Calculations show that a sample size of 110 participants would provide 80% power to determine that 60% ($\pm 6\%$) of the participants will achieve pain relief at 2 hours post-treatment. The sample size may be increased to up to 130 participants to account for a potential ~15% drop-out rate and/or missing data.

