7.4. Analysis sets

Intent to treat analysis set (ITT)

The ITT analysis set includes all patients undergoing the treatment phase.

Modified intend to treat analysis set (mITT)

The mITT analysis set includes all patients undergoing the treatment phase and treat a test treatment within 60 minutes of attack onset. Subjects with no valid post baseline assessment will not be included in the relevant analysis.

Per-protocol analysis set (PP)

The PP analysis set includes all patients from the mITT analysis set without major protocol deviations. Main protocol instructions include:

- has started within 60 minutes of attack onset
- was administered to treat a qualifying migraine attack
- was administered for at least 30 minutes
- includes data on pain intensity at 2 hours post-treatment
- rescue medication was not used before or within 2 hours post-treatment

Nerivio TCH-004 Clinical Study Protocol (NCT04089761)

Doc ID: TEC0105

Revision #: 1.0

Page: 36 of 49

Statistical analysis of the analysis sets

The ITT analysis set will serve as the main set for safety assessments.

The mITT analysis set will serve as the primary set for the efficacy assessment.

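### Participants who use the device once and stop are in no efficacy denominator, and the optional imputations in 7.5.6 name no analysis set that would bring them back

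*Combined protocol and SAP*

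**What the plan says.** Section 7.5.4 treats the first device use as training and excludes it from efficacy. The first treated qualifying attack after it is the test treatment, the source of all efficacy results. If that treatment has no 2-hour pain score, a later evaluable one takes its place.

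Section 7.4 defines the efficacy set: "The mITT analysis set includes all patients undergoing the treatment phase and treat a test treatment within 60 minutes of attack onset". Subjects without a valid post-baseline assessment are also left out of the relevant analysis. The synopsis assigns efficacy to mITT without exception; 7.4 calls mITT the primary efficacy set. ITT is assigned to safety and tolerability.

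Section 7.5.6 lists sensitivity analyses that may be performed for missing 2-hour pain data. Under Dropout/AE, a subject with no post-baseline pain measurement is a non-responder, and "a subject withdrawn due to an adverse event or treatment intolerability should be considered as a non-responder for this analysis". Worst Case counts all subjects with missing pain data as failures. Observed data would "use only treatments with non-missing pain data who did not withdraw early from study". None of these names an analysis set.

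**The concern.** Someone who tries the device once and does not want to use it again is the kind of participant a non-responder analysis should count. Under these definitions that person has no test treatment, so is outside mITT and outside its per-protocol subset. If 7.5.6 is run on mITT, the Dropout/AE rule reaches only those who went on to a second treated attack. The replacement rule in 7.5.4 also leaves few missing scores to impute.

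The trial has one arm, so there is no comparator in which the same loss could cancel. The response rate would describe adolescents who carried on after a first try, and the check on withdrawal could leave out the earliest withdrawals.

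The Observed data option has a separate fault. It drops a valid 2-hour score because the participant withdrew afterwards, so inclusion depends on something that happens after the outcome.

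**Working it through.** **1. The plan's own figures (7.3).** Inputs: 60% response, ±6 points, 110 participants, and "The sample size may be increased to up to 130 participants to account for a potential ~15% drop-out rate and/or missing data".
- n = z²p(1−p)/h² = 1.2816² × 0.60 × 0.40 / 0.06² = 109.5, so 110. This reproduces 110 as a two-sided 80% confidence half-width.
- 110/(1 − 0.15) = 129.4, so 130. The planned loss is 130 − 110 = 20 participants (15.4%).
- At 60% response, 0.60 × 110 = 66 responders: 66/110 = 60.0% (95% exact CI 50.2 to 69.2).

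**2. Who is counted, from 7.4, 7.5.4 and 7.5.6.**

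| Participant | In mITT? | Reached by 7.5.6 on mITT? |
|---|---|---|
| Training use only, then stops | No | No |
| Test treatment unscored, later evaluable treatment exists | Yes, through the replacement | Nothing left to impute |
| No post-training treatment has a 2-hour score | Meets the definition, but left out of the relevant analysis | Yes |
| Valid 2-hour score, later withdraws for AE or intolerability | Yes | Yes: Dropout/AE makes it non-response; Observed data drops it |

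**3. The adult study (4.2.2).** In the active arm, 126 were assigned and 99 analysed, so 27 were not. Section 4.2.2 gives the worst-case result as "66/103=64.1% for active versus 41/104=39.4% for sham". That restored 103 − 99 = 4 of the 27 and left out 126 − 103 = 23 (23/126 = 18.3%). The rate moved from 66/99 = 66.7% to 64.1%. Across both arms, 237 completed at least one treatment and 203 the test treatment: (237 − 203)/237 = 34/237 = 14.3%.

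**4. Size here, counting only reasons that resemble stopping the device.** Adult counts, pooled over 252:
- Narrow: 3 intolerance + 4 own decision = 7; 7/252 = 2.8%. Scaled to 130: 3.6, about 4.
- Wide: add 6 other and 9 unknown = 22; 22/252 = 8.7%. Scaled to 130: 11.3, about 11.

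Adding these to the 110 as non-responders:
- 66/(110 + 4) = 66/114 = 57.9%, a fall of 2.1 points.
- 66/(110 + 11) = 66/121 = 54.5%, a fall of 5.5 points.

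**5. Lower bound.** Counting all 20 planned losses as failures gives 66/130 = 50.8% (41.9 to 59.6), a fall of 9.2 points. The bound depends on the planned loss. With the response among those treated held near 60%, a loss of 10% gives 70/130 = 53.8% and a loss of 20% gives 62/130 = 47.7%.

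**The case against.** **The imputations may be meant for ITT.** Section 7.5.6 speaks of subjects withdrawn and of all subjects with missing pain data, without limiting them to mITT, and 7.4 calls mITT only the primary efficacy set. A reader might infer that the imputations cannot reach early stoppers. The documents do not support that, because the set is simply not stated. What stands is that two readings give different rates and the plan does not choose between them. Even on the wider reading, a participant who stops for no benefit or by choice, with pain scores from the training treatment, is not clearly caught by Dropout/AE.

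**The large falls measure something else.** A reader might take 66/126 = 52.4% in the adult active arm, or 66/130 = 50.8% here, as the effect of early stopping. Neither is. In the adult study, 18 of the 37 participants who "were excluded from the efficacy analyses" for lack of a test treatment had too few attacks, 4 participants were lost to follow-up, and 252 − 237 = 15 had completed no treatment. The study also reports no withdrawals due to adverse events and has no category for lack of benefit, so those two reasons cannot be sized. This objection stands, and it is why the narrower range leads.

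**Withdrawals are visible elsewhere.** Efficacy is secondary. Section 7.5.3 reports non-completion overall and because of adverse events, with Kaplan-Meier curves of time to withdrawal. That is true, but these tables do not enter the response rate, and they miss a participant who stays enrolled and stops using the device.

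**Conclusion.** The point holds as a gap in specification. Training-only users are in no mITT denominator, and 7.5.6 neither requires a supporting analysis nor names a set that includes them. The expected effect on a planned 60.0% is a fall of about 2 to 5.5 points, to between 57.9% and 54.5%.

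This range assumes that adult reasons, pooled over active and sham, carry over to adolescents. It also assumes that those counted had used the device at least once, which the adult report does not show for each of them. The 50.8% figure is a lower bound for the planned loss of 20, and should not be read as an estimate.

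Nothing here shows that mITT is the wrong primary set, or that the true response is near 50%. The Observed data clause is a smaller, separate fault in one optional analysis.

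**What to change.** In 7.5.6:
- State that the Dropout/AE and Worst Case analyses of 2-hour pain relief and pain freedom will be run, on all ITT participants with at least one device use, including the training treatment.
- In Dropout/AE, also count as non-responders those with no test treatment because of an adverse event, intolerance, lack of benefit or a decision not to use the device.
- In Worst Case, also count everyone with no test treatment, including unknown reasons and too few qualifying attacks.
- Report both beside the mITT rate, which stays primary. Record and tabulate the reason for each missing test treatment.
- In the Observed data definition, delete the clause about early withdrawal, so that a valid 2-hour score is kept whatever happens later.

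The cost is wording, one extra table, and one reason field if it is not already collected; the documents do not show that it is. Section 9.1 lets a separately held SAP change without a protocol amendment, but editing section 7 itself would need one. The visible downside is a lower supporting response rate beside the mITT figure.
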